6. PATIENT SELECTION/ELIGIBILITY CRITERIA

6.1 Inclusion (Eligibility) Criteria

- The patient must be able willing and able to provide informed consent.
- The patient is a male between ≥ 30 and ≤ 80 years of age.
- The patient has ED of Vasculogenic origin determined by penile duplex ultrasound.
- The patient is PDE5i responsive, meaning he is able to achieve and maintain an erection under the effect of the maximal dosage of PDE5i.
- The patient has been in a stable heterosexual relationship for over 3 months prior to enrollment.
- A minimum of 2 sexual attempts per month for at least one month prior to enrollment – as documented by the Sexual Health Questionnaire (SHIM).
- The patient is suffering from erectile dysfunction lasting for over 6 months and not more than 5 years as per history provided by patient.
- IIEF-EF score between 11 and 25.
- Testosterone level 300-1000 ng/dL within 1 month prior to enrollment.
- A1C level $\leq 7\%$ within 1 month prior to enrollment.
- Patients have at least a natural tumescence during sexual stimulation (EHS score ≥ 1).

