7. STUDY DESIGN, CLINICAL, RADIOLOGICAL, LABORATORY AND SURGICAL EVALUATIONS

7.1 Study Design

This is a prospective, randomized, clinical study aimed to evaluate the safety and efficacy of the two treatment schedules on symptomatic ED patients. The patients are randomized in a 1:1 ratio into two active treatment groups. (Refer section 18)

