10.4 Sample size, accrual and study duration

TOTAL SAMPLE SIZE: 80
TOTAL ACCRUAL: 80
ACCURAL DURATION: 12 MONTHS
STUDY DURATION: 7 months

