10.5 Statistical Analysis and Power calculation

The average and standard deviation of all relevant variables, including demographic and baseline characteristics, primary and secondary outcomes will be calculated.

IIEF-EF and EHS scores will be analyzed using ANOVA with repeated measures throughout the study, in order to compare the trends of groups A and B.

GAQ, SEP and success rates will be analyzed and compared between the groups according to Fisher's exact test in each of the endpoints. The statistical significance will be set at $P < 0.05$.

Demographic characteristics such as age and ED duration will be compared between groups A and B using student's test. Other demographic characteristics, such as medical background and risk factors will be compared between these groups using Fisher's exact test.

A sample of 80 men with failing scores on the IIEF SEP2 question will be randomized 1:1 into one of two arms (low intensity or high intensity treatment) using a permuted random block algorithm. We hypothesize that following placebo treatment between 0 and 5% of men will pass the SEP2 question and at least 35% of men treated at either intensity level will pass. We have two co-primary

endpoints, the percentage of men passing after low intensity and high intensity relative to placebo, which will be assessed by two independent Fisher’s exact tests. Each of these tests will be conducted with a 0.025 alpha error level to allow for a 0.05 experiment wide type I error rate. Power calculations done in SAS 9.4 suggest that with 40 men randomized into each group we will have at least 85% power to detect the difference between a 5% and 35% response rate. So long as our non-compliance/drop-out rate remains above 10% will will have at least 80% power (see Figure 1).

Computed N per Group			
Index	Nominal Power	Actual Power	N per Group
1	0.80	0.813	37
2	0.85	0.852	40
3	0.90	0.900	45

Figure 1. Sample size needed for 80% 85% and 90% nominal power for a Fisher’s exact test with alpha = 0.025 (using an exact conditional distribution with the Walters normal approximation method).

10.6 Randomization:

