80 patients will be randomized 1:1 to treatment groups with 40 patients each. An online based randomization tool called randomized.org will be used. This will be prepared beforehand, with treatment option printed on the paper and then sealed in an envelope (80 envelopes). Each would have Patients ID number printed out side and randomization information inside. This would be opened after a patient has signed the informed consent and is ready to receive treatment. The PI nor the study coordinator will not have the knowledge of patient’s treatment group beforehand.

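### Section 10.5 sets two co-primary SEP2 tests against placebo with 85% power, but the trial has only two active arms, so the tests cannot be run and n = 80 has no valid basis

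*Combined protocol and SAP*

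**What the plan says.** **Design.** Section 7.1: "The patients are randomized in a 1:1 ratio into two active treatment groups". Section 7.4 describes only Groups A and B, both receiving shocks at treatment energy. Section 10.4 gives "TOTAL SAMPLE SIZE: 80", and section 10.6 accounts for all of them: "80 patients will be randomized 1:1 to treatment groups with 40 patients each".

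**Power paragraph of section 10.5.** "A sample of 80 men with failing scores on the IIEF SEP2 question will be randomized" to low or high intensity. The expected SEP2 pass rate is 0 to 5% on placebo and at least 35% at either intensity. The co-primary endpoints are "the percentage of men passing after low intensity and high intensity relative to placebo, which will be assessed by two independent" Fisher's exact tests, each at 0.025. The paragraph then states that "with 40 men randomized into each group we will have at least 85% power" for 5% versus 35%. Figure 1 gives power 0.813, 0.852 and 0.900 at 37, 40 and 45 per group.

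**Endpoints elsewhere.** Sections 3.1 and 10.1 make IIEF-EF primary; sections 3.2 and 10.2 make SEP secondary. The null hypothesis in section 2.2 concerns change from baseline.

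**Other analyses in section 10.5.** IIEF-EF and EHS go into "ANOVA with repeated measures throughout the study, in order to compare the trends of groups A and B". GAQ, SEP and success rates are compared between the groups by Fisher's exact test at P < 0.05.

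**The concern.** The declared co-primary tests need placebo data that the trial will not collect. The only justification for 80 men rests on those tests, so it supports none of the analyses that can be run. IIEF-EF has no sample-size basis at all.

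The primary contrast is also left open. Section 2 points to change from baseline, which has no control. Section 10.5 points to a comparison of A and B over time without naming a visit or model term. If this is not settled beforehand, the contrast can be chosen after the data are seen, and a within-arm gain could be presented as efficacy.

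The same paragraph departs from the rest of the protocol in other ways:
- It makes SEP2 co-primary.
- It presumes that all men fail SEP2 at entry, whereas the relevant criterion in section 6.1 is "IIEF-EF score between 11 and 25".
- It labels the arms by intensity, whereas section 7.4 defines two schedules with equal totals (5 × 720 = 6 × 600 = 3,600 shocks per region).
- Its attrition sentence promises 80% power if drop-out stays above 10%, which reverses the direction.

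**Working it through.** **1. Reproduce Figure 1.** Inputs from section 10.5: p1 = 0.05, p2 = 0.35, alpha 0.025, equal groups, Walters approximation. Sidedness is not stated; two-sided reproduces the table.

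Power = Φ( √(2n) × [asin√(p2 − 1/(2n)) − asin√(p1 + 1/(2n))] − 2.2414 )

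At n = 40: asin√0.3375 = 0.6199 and asin√0.0625 = 0.2527. The difference is 0.3672; times √80 this is 3.284. Φ(3.284 − 2.241) = 0.852.

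| n per group | Walters | Figure 1 |
|---|---|---|
| 37 | 0.813 | 0.813 |
| 40 | 0.852 | 0.852 |
| 45 | 0.900 | 0.900 |

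Exact enumeration of Fisher's test at n = 40 gives 0.850. At 36 per group (10% loss), Walters gives 0.799 and exact Fisher 0.821. The calculation is correct for 40 active versus 40 placebo men.

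**2. Count the arms.** 40 in A + 40 in B = 80, the whole sample. That leaves 0 men for placebo.

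**3. Could 5% be a fixed benchmark?** That would be a one-sample exact binomial test with n = 40. Probability of reaching the cut-off:

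| Cut-off | True rate 5% | 35% (power) | 10% | 15% | 20% |
|---|---|---|---|---|---|
| ≥ 7/40 (upper tail ≤ 0.0125) | 0.003 | 99.6% | 10% | 39% | 71% |
| ≥ 6/40 (upper tail ≤ 0.025) | 0.014 | 99.9% | 21% | 57% | 84% |

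Neither cut-off gives 85%. The last three columns show how often the test would pass with no treatment effect if the untreated rate were 10, 15 or 20%. Those rates are assumptions, but entry does not require SEP2 failure, so eligibility does not secure a rate of 0 to 5%.

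**4. SEP2, A versus B** (exact Fisher, two-sided 0.05). The only active rate in the documents is 35%; all other rates are illustrative assumptions.

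| Rates | 40 per arm | 36 per arm |
|---|---|---|
| 35% vs 35% | 2.8% | 2.7% |
| 35% vs 50% | 21% | 17% |
| 35% vs 60% | 55% | 46% |
| 35% vs 68% | 81% | 73% |
| 50% vs 82% | 82% | 77% |
| 70% vs 95% | 82% | 76% |
| 35% vs 8% | 81% | 75% |

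The first row sets both arms at the plan's own 35%; there is then no difference to detect.

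**5. IIEF-EF, A versus B.** 95% CI half-width = t(0.975, 78) × SD_c × √(2/40) = 1.991 × 0.2236 × SD_c = 0.445 × SD_c. The documents give no labelled SD or correlation. I assume an SD of 4 to 8 points, equal at all visits, and a within-man correlation r of 0.4 to 0.8 between any two visits.

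| Contrast | SD_c | Half-width, points |
|---|---|---|
| Raw score, one visit, unadjusted | SD | 1.8 to 3.6 |
| Change from baseline, one visit | SD√(2(1−r)) | 1.1 to 3.9 |
| Mean change, months 1, 3, 6 | SD√((1+2r)/3 + 1 − 2r) | 0.9 to 3.2 |
| Baseline-adjusted three-visit mean | SD√((1+2r)/3 − r²) | 0.9 to 2.4 |

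Example: SD 8, r = 0.4, change at one visit: 0.445 × 8 × √1.2 = 3.9. At 36 per arm, change at one visit is 1.2 to 4.1 and three-visit mean change 1.0 to 3.4.

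**The case against.** The strongest reply is that an impossible test cannot produce a false positive, that sections 2 and 3 make no placebo claim, and that the endpoint hierarchy is clear outside this one paragraph. On that view the paragraph is leftover text and the harm is small. Part of this stands: the endpoint itself is not in doubt. But the paragraph is the only declared co-primary analysis and the only basis for n = 80, so setting it aside leaves the sample size unjustified.

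A second reply is that comparing trends in a repeated-measures ANOVA ordinarily means the group-by-time interaction, so a contrast exists. That is a fair reading, but the plan does not say so, and section 2 tests something else.

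Third, the plan never mentions a fixed benchmark, and the result of such a test depends on the cut-off. That is true. Both cut-offs are shown, and the check serves only to rule that reading out.

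Fourth, the contradiction could be resolved the other way, by adding a placebo or sham arm. It could, but keeping the stated power would need 40 men in each of three arms, 120 in total. Spreading 80 men over three arms (26 or 27 each) gives 60 to 63% by Walters, or 63 to 66% by exact Fisher.

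The section 18 flowchart is not reproduced in the text available. The wording of sections 7.1, 7.4, 10.5 and 10.6 is explicit and agrees on two active arms.

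**Conclusion.** Wrong as written, and it must be fixed. The fault is the missing comparator, not the arithmetic: 0.852 is right for 40 active versus 40 placebo men, and the trial has no placebo men. The co-primary tests cannot be run, and the 85% applies to no contrast the trial hypothesises.

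The randomised contrast that exists detects only large SEP2 differences: 21% power for 35% versus 50%, and about 80% only for gaps of roughly 25 to 33 percentage points, depending on the rates. For IIEF-EF, the half-width for A minus B lies between about 0.9 and 3.9 points, depending on the contrast, SD and correlation.

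The contradiction and the reproduction of Figure 1 rest on the documents alone, apart from taking the test as two-sided. The A-versus-B powers rest on assumed pass rates, and the IIEF-EF widths on assumed SDs and correlations.

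**What to change.** 1. Delete from section 10.5 the placebo co-primary tests, the 0.025 split, the 85% power statement, Figure 1 and the attrition sentence that depends on them.
2. Keep IIEF-EF primary and SEP2, SEP3, GAQ and EHS secondary, as sections 3 and 10.1 to 10.2 have it. State that A versus B is the only randomised contrast. The sponsor then names one contrast within the planned repeated-measures analysis, with a 95% CI: for example the A−B difference in change from baseline at one named visit, or in mean change over months 1, 3 and 6.
3. State that change from baseline (section 2) is a within-arm, uncontrolled result that cannot support a claim relative to placebo. Sections 7.3 and 7.4 contradict each other on PDE5i use during follow-up; they must be reconciled before that change can be interpreted.
4. Replace the 85% claim with what 40 per arm gives: the SEP2 powers above, and the IIEF-EF half-width for the contrast chosen in step 2. Label the assumed rates, SDs and correlations, and label any unadjusted single-visit figure as such. Repeat at the expected number of completers.
5. If a comparison with 5% is kept, describe it as a non-randomised one-sample exact binomial test against an assumed rate, and state sidedness and cut-off. In either case, state whether failing SEP2 is an entry condition, because sections 6.1 and 10.5 differ.
6. Reconcile the intensity labels in section 10.5 with the schedules in section 7.4.

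**Cost.** A protocol amendment, because a declared co-primary analysis and the sample-size justification are replaced. The stated power becomes less favourable, and no efficacy claim relative to placebo remains. No patients or visits are added. If the sponsor wants the placebo claim, that is a different trial: 120 men over three arms on the plan's own assumptions.

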3. OBJECTIVES

3.1 Primary Efficacy Objective

To evaluate change of IIEF-EF score⁹ from baseline to follow-ups 1, 3 and 6 months' post treatment (appendix I).

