10. STATISTICAL CONSIDERATIONS

10.1 Primary Study Endpoints

The IIEF-EF questionnaire (appendix I) was chosen as the primary clinical efficacy assessment tool in this study. The total score (range 0-30) will be used for statistical analysis.

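### The 0.05 experiment-wide error rate in Section 10.5 covers only two SEP2-versus-placebo tests that a trial without a placebo arm cannot run; the declared primary, IIEF-EF, and the A-versus-B tests lie outside it

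*Combined protocol and SAP*

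**What the plan says.** The plan gives two accounts of what is primary.

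- **IIEF-EF.** Section 3.1 sets the primary objective: "To evaluate change of IIEF-EF score⁹ from baseline to follow-ups 1, 3 and 6 months' post treatment". Section 10.1 agrees: "The IIEF-EF questionnaire (appendix I) was chosen as the primary clinical efficacy assessment tool in this study". Section 10.5 gives the method, "IIEF-EF and EHS scores will be analyzed using ANOVA with repeated measures throughout the study", with the aim of comparing the trends of groups A and B.
- **SEP2.** Later in Section 10.5 the co-primary endpoints are "the percentage of men passing after low intensity and high intensity relative to placebo", tested by two Fisher's exact tests. The alpha statement follows: "Each of these tests will be conducted with a 0.025 alpha error level to allow for a 0.05 experiment wide type I error rate". Sections 3.2 and 10.2 list SEP questions 2 and 3 as secondary, with GAQ and EHS.

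For the other binary outcomes Section 10.5 says "GAQ, SEP and success rates will be analyzed and compared between the groups according to" Fisher's exact test, and then "The statistical significance will be set at $P < 0.05". That is the only general significance level in the document. Section 7.5 sets follow-up visits at months 1, 3 and 6, and Section 10.2 places SEP, GAQ and EHS at follow-ups.

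The document gives no test order, no alpha split between IIEF-EF and SEP2, and no statement that secondary tests lie outside error control. Sections 7.1, 7.4 and 10.6 describe randomization to two active groups of 40.

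**The concern.** An experiment-wide rate is a statement about all the tests on which the trial will base its claims. Here the whole 0.05 goes to two SEP2 tests, while the endpoint that the protocol elsewhere calls primary has no allocation. A reader of the eventual report could take the 0.05 as covering the IIEF-EF result and the comparison of schedules, and it covers neither.

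The trial's randomized question is whether the two schedules differ. With several binary questionnaire items, up to three visits and no stated hierarchy, one chance result on one item at one visit could be reported as showing that one schedule is better, under a protocol that promises 5% error.

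**Working it through.** **1. The plan's own figures.** Inputs from Section 10.5: two tests at 0.025, response 5% versus 35%, 40 per group.

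- Alpha: 0.025 + 0.025 = 0.05. The stated rate is correct for these two tests.
- Power, by the Walters approximation named under Figure 1 (two-sided alpha 0.025; sidedness is not stated, but two-sided reproduces the figure): Φ(√(n/2) × 2[asin√(0.35 − 1/2n) − asin√(0.05 + 1/2n)] − 2.241). At n = 40 this is Φ(4.472 × 0.734 − 2.241) = Φ(1.04) = 0.852. The same formula gives 0.813 at n = 37 and 0.900 at n = 45. All three match Figure 1.

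**2. What the 0.05 covers.**

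| Test | Where | Level | Inside the stated 0.05? | Can be run? |
|---|---|---|---|---|
| SEP2, each schedule versus placebo (2 tests) | 10.5 | 0.025 each | Yes | No: no placebo arm |
| IIEF-EF, A versus B, repeated-measures ANOVA | 3.1, 10.1, 10.5 | 0.05, by inference | No | Yes |
| EHS, A versus B, repeated-measures ANOVA | 3.2, 10.2, 10.5 | 0.05, by inference | No | Yes |
| SEP, GAQ and success rates, A versus B, Fisher | 3.2, 10.2, 10.5 | 0.05 | No | Yes |

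The tests inside the stated rate are exactly those that the design cannot supply.

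**3. Size of the uncontrolled part.** Count SEP2, SEP3 and GAQ-Q1 at three visits: 3 × 3 = 9 Fisher tests. GAQ-Q2 is left out because Appendix III asks it only of men who answered yes to Q1, so it is not a comparison of 40 with 40.

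Fisher's test is conservative. By full enumeration at 40 per arm and nominal 0.05, its actual size is about 0.028 at a common response rate of 35% and 0.033 at 50%. If the nine tests were independent:

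- at 35%: 1 − (1 − 0.028)^9 = 0.23
- at 50%: 1 − (1 − 0.033)^9 = 0.26

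The tests will be positively correlated, which lowers these figures. I simulated nine correlated binary outcomes in two arms of 40 with no true difference (20,000 runs per setting):

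| Latent correlation between items / between visits | 35% response | 50% response |
|---|---|---|
| 0 / 0 | 23% | 26% |
| 0.5 / 0.5 | 20% | 24% |
| 0.7 / 0.8 | 17% | 20% |
| 0.9 / 0.9 | 13% | 15% |

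The range is about 13-26%.

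**The case against.** The strongest reply is that the sentence speaks only of the two tests before it and divides alpha correctly between them, that SEP, GAQ and EHS are already labelled secondary, and that plans commonly leave secondary tests uncontrolled. Much of this stands. The arithmetic is right, and a plan may leave secondary endpoints uncontrolled if it says so. This one does not, and it calls the rate experiment-wide. The reply also does not reach IIEF-EF, which is a declared primary outside the split.

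Three stronger readings are tempting, and the documents do not support them.

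- *The primary-level error rate is 0.10* (0.025 + 0.025 + 0.05). This adds two placebo comparisons that the trial cannot make to an IIEF-EF level that is itself inferred: the P < 0.05 sentence stands in the paragraph on GAQ and SEP. It is not a rate that this trial can have.
- *Twelve Fisher tests give 46%* (1 − 0.95^12). This assumes independence and an exact size of 0.05 for each test, and it counts GAQ-Q2 as a full comparison. None of these holds.
- *The primary result can be picked from three visits.* For IIEF-EF, Section 10.5 plans one repeated-measures analysis of the two groups' trends. The lack of a named visit matters mainly for the secondary items.

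It may also be said that the missing placebo arm is the more basic fault. It is, but correcting it alone would still leave IIEF-EF outside the split and SEP2 classified in two ways.

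**Conclusion.** The concern holds in this form: the 0.05 rate in Section 10.5 is correct only for two SEP2-versus-placebo tests, those tests cannot be run as randomized comparisons, and neither the declared primary nor any A-versus-B comparison is covered. SEP2 is co-primary in 10.5 and secondary in 3.2 and 10.2, and the two must be reconciled.

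The uncontrolled SEP and GAQ comparisons carry about a 13-26% chance of at least one nominally significant result when the schedules do not differ. That range assumes nine tests, with testing at each visit inferred from Sections 7.5 and 10.2 because Section 10.5 names no visit; 40 men per arm with complete data; response of 35-50%, the lower value being the minimum that Section 10.5 expects under active treatment; and latent correlations from 0 to 0.9. Much lower response would reduce it, because Fisher's test becomes very conservative. EHS and the undefined success rates are not counted.

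This should be corrected, but it does not by itself invalidate the comparison of schedules.

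**What to change.** - Name IIEF-EF as the only primary endpoint, with one pre-specified A-versus-B test at 0.05: either the group-by-time test of the planned repeated-measures ANOVA or a comparison at one named visit. The planned ANOVA already supplies a single test, so naming one visit is optional.
- List SEP2 as secondary throughout. Delete the 0.025 split and the experiment-wide sentence.
- State that SEP, GAQ, EHS and success-rate comparisons are secondary without error control, and report them as estimates with 95% confidence intervals and nominal p-values.
- Align Section 2, whose hypotheses concern change from baseline within the treatment groups, with the chosen primary test.

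**Cost.** No added patients or data, but more than a wording change. Isolated secondary results can no longer be claimed as confirmatory. The 5% versus 35% power statement no longer supports the primary test, so the detectable IIEF-EF difference or expected precision at 40 per arm must be restated under an assumed SD.

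As an illustration for a single-visit comparison at two-sided 0.05 and 80% power: (1.960 + 0.842) × SD × √(2/40) = 0.63 SD. If the 5.8 and 4.1 printed beside the IIEF means in Section 1.4 are taken as SDs, which is an assumption, this is 2.6 points at SD 4.1 and 3.6 points at SD 5.8. The SD of change scores may differ, and the sponsor should justify the value used.

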5.3 Cancellation Guidelines

The following are reasons for withdrawal of subjects from the study:

- A subject does not meet the eligibility criteria; (the subject will be considered a screen failure).
- A subject withdraws consent,
- A subject die's during protocol participation from causes other than the study treatment (not due to adverse events) or
- A study investigator decides the subject should be withdrawn from the study (e.g. subject non-compliance)

Regardless of reason for withdrawal, once a patient has been randomized to an arm, an intention to treat analysis will be performed.

All subjects who either screen fails, is withdrawn from the study or has completed all visits should be de-enrolled from the research database within 48 hours.

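### The drop-out condition in the power statement is reversed: 80% power holds when loss stays below 10%, not above it

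*Combined protocol and SAP*

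**What the plan says.** Section 10.5 plans Fisher's exact tests of each treatment intensity against placebo: "Each of these tests will be conducted with a 0.025 alpha error level". It claims that "with 40 men randomized into each group we will have at least 85% power", where the effect is given as "power to detect the difference between a 5% and 35% response rate". It then sets a tolerance for loss: "So long as our non-compliance/drop-out rate remains above 10% will will have at least 80% power", and refers to Figure 1. That table lists 37, 40 and 45 men per group for nominal power of 80%, 85% and 90%, with actual power of 0.813, 0.852 and 0.900, computed "using an exact conditional distribution with the Walters normal approximation method".

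Section 10.6 fixes the allocation: "80 patients will be randomized 1:1 to treatment groups with 40 patients each". On withdrawals, section 5.3 says that "once a patient has been randomized to an arm, an intention to treat analysis will be performed".

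**The concern.** Losing men lowers power, so a guarantee of 80% cannot depend on the loss rate being above a threshold. Read literally, the sentence promises 80% power in the range of loss where the plan's own method falls short of it, and makes no promise where 80% does hold.

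This is the only tolerance for loss in the documents. The accrual goal of 80 equals the 40 per group in the power calculation, with no extra men for drop-out, and follow-up runs for six months. Anyone who judges whether the observed loss was acceptable, or who copies the power statement into a report, will use this sentence.

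**Working it through.** **Inputs.** All are from section 10.5 unless noted: response rates 5% and 35%; alpha 0.025 per test; Fisher's exact test with the Walters approximation; 40 men per group (also section 10.6). Sidedness is not stated. Two-sided is inferred because it reproduces Figure 1; a one-sided 0.025 test would give 0.879 at 37 per group, not 0.813.

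**Formula.** With n per group,

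power = Φ( √(2n) × [arcsin √(0.35 − 1/(2n)) − arcsin √(0.05 + 1/(2n))] − z ), where z = z(1 − 0.025/2) = 2.2414.

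**Step 1: reproduce Figure 1.** At n = 37 the two arcsines are 0.6188 and 0.2548. Then √74 × 0.3641 = 3.132, 3.132 − 2.241 = 0.890, and Φ(0.890) = 0.813. The same formula gives 0.852 at n = 40 and 0.900 at n = 45. All three rows match.

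**Step 2: power as men are lost from 40 per group and removed from the analysis.** The last column enumerates all outcomes of the two-sided Fisher test.

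| Lost per group | Loss | Left | Walters | Exact Fisher |
|---|---|---|---|---|
| 0 | 0% | 40 | 0.852 | 0.850 |
| 2 | 5% | 38 | 0.827 | 0.840 |
| 3 | 7.5% | 37 | 0.813 | 0.825 |
| 4 | 10% | 36 | 0.799 | 0.821 |
| 5 | 12.5% | 35 | 0.784 | 0.803 |
| 6 | 15% | 34 | 0.767 | 0.784 |
| 8 | 20% | 32 | 0.732 | 0.742 |

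Above 10% loss, power is under 80% throughout by Figure 1's method. By exact enumeration it is under 80% from 15% loss.

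**Step 3: test the threshold with the direction corrected.** 10% of 40 is 4, so a loss strictly below 10% is at most 3 men per group. 40 − 3 = 37, which is Figure 1's row for 80%, with power 0.813.

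**Step 4: men kept in the analysis.** Step 2 removes lost men. Under intention to treat they stay in, but the documents give no rule for a missing SEP2 answer. Two assumptions, both at n = 40 and 10%:

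- Lost men count as failures, equally in both groups. The rates become 0.9 × 5% = 4.5% and 0.9 × 35% = 31.5%. Power is 0.789 (Walters) or 0.779 (exact).
- 10% of treated men do not comply and respond at the 5% rate. The treated rate becomes 0.9 × 35% + 0.1 × 5% = 32%, against 5%. Power is 0.775 (Walters) or 0.766 (exact).

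**The case against.** The strongest defence is that this is an obvious slip. The sentence also contains a doubled word, the table beside it shows power rising with sample size, and no replacement or stopping rule hangs on the figure. Nobody would set out to lose more than 10% of the men. This limits the harm, but the sentence still states a power property that the design does not have.

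A reader might go further and infer that the 10% figure is itself wrong, because 10% of 40 leaves 36 and Figure 1 asks for 37. The documents do not support that. A loss below 10% leaves at least 37. Even at exactly 10%, power is 0.799 by Walters, about 0.1 percentage point short, and 0.821 by exact enumeration of the test the plan names.

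A reader might also infer from section 5.3 that true power at 10% loss is about 78%. That figure needs lost men to be scored as failures, at the same rate in both groups. Section 5.3 promises intention to treat but does not say how missing answers are scored, so the figure is a scenario and not a property of the plan.

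The last objection is the weightiest: the whole calculation compares each intensity with placebo, while sections 7.1, 7.4 and 10.6 describe only two active groups. None of these power figures describes a comparison that the trial can make. That stands, and it is a larger problem than this sentence. It is no reason to carry a reversed condition into the next version of the power statement.

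**Conclusion.** The direction of the drop-out condition is wrong, and this is certain from the text. Its size, by Figure 1's own method, is power of 0.784, 0.767 and 0.732 at losses of 12.5%, 15% and 20%, where the sentence promises at least 0.80. The exact values are 0.803, 0.784 and 0.742.

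The 10% threshold and the sample size are not materially wrong on the plan's own terms. This rests on rates of 5% and 35%, a two-sided alpha of 0.025 (inferred), and removal of lost men from the analysis. If they are kept in, power at 10% is about 0.78 to 0.79 or about 0.77 to 0.78 under the two scenarios above, both of which are assumptions. It is a small error, but it sits in the power statement.

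**What to change.** Replace the sentence in section 10.5 with: *Power is at least 80% so long as drop-out remains below 10% (no more than 3 of 40 men lost per group, leaving the 37 in Figure 1).* Stating the count per group removes any doubt about how the rate relates to the table.

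If the authors want to cover non-compliance or men kept in under intention to treat, they should add the figure with its assumption named, and say how a missing SEP2 answer is scored.

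When the power statement is re-based on a comparison that the two active groups can make, carry over the corrected direction and recompute the tolerance for that comparison.

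The cost is one sentence. No extra patients are needed, and the intended tolerance does not change.
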